1 PROTOCOL SUMMARY

[figure not shown]
1.1 SYNOPSIS

Title:	OUTLAST: A Phase 2, Double-Blind, Randomized, Placebo-Controlled, Multiple-Dose Study to Evaluate the Safety and Efficacy of IXT-m200 in Treatment-Seeking Individuals with Methamphetamine Use Disorder
Study Description:	This Phase 2 study will evaluate the safety and efficacy of monthly intravenous doses of IXT-m200 in treatment-seeking individuals with methamphetamine (METH) use disorder (MUD). The hypotheses are that treatment with IXT-m200 will reduce the occurrence of stimulant-positive samples compared to placebo (following an initial grace period during which relapses may occur) and improve the signs and symptoms of MUD .
Objectives:	Primary Objective: To evaluate the efficacy of IXT-m200 in preventing or reducing relapse to stimulant use . Secondary Objectives: To evaluate the efficacy of IXT-m200 in improving the signs and symptoms of MUD, increasing the number achieving early remission, improving the proportion of participants achieving stimulant abstinence, improving participant-rated quality of life, and to evaluate the safety of multiple intravenous doses of IXT-m200 .
Endpoints:	Primary Endpoint: 
Percent of 20 weeks abstinent from stimulants following a 4-week grace period (between Week 5 and Week 25) as measured by saliva screens and by self-report via smartphone app. Secondary Endpoints: 
Proportion of responders at Week 25 as measured by DSM-5 criteria. A responder is a participant who meets the definition of early remission, i.e., ≥ 3 months and < 12 months without meeting DSM-5 criteria while disregarding the result for craving.Complete abstinence during the last month of study drug treatment (between Week 21 and Week 25), as measured by saliva screens and by self-report via smartphone app.Change from screening in participant-rated quality of life as measured by the Treatment Effectiveness Assessment (TEA) at Weeks 13, 25, and 33.Safety and tolerability of IXT-m200 assessed by physical examinations and vital sign, AE, ECG, and clinical laboratory testing.Number of participants with anti-IXT-m200 antibody levels that are confirmed positive and have titers more than three times the minimum required dilution. Exploratory Endpoints: 
Number of sequential weeks of abstinence from the end of treatment visit (Week 25), defined as four weeks after the final planned treatment visit (Week 21) as measured by saliva screens and by self-report via smartphone app.Point-prevalence abstinence (last 7 days) as measured by saliva screens and by self-report via smartphone app at Week 25, Week 29, and Week 33.

- Weekly abstinence from stimulants following a 4-week grace period (between Week 5 and Week 25) as measured by saliva screens.
- Difference between number of adverse outcomes recorded between Week 5 and Week 33. Adverse outcomes include those queried in the Adverse Outcomes Assessment and also suicide and overall mortality.
- Proportion of responders at Week 33 as measured by DSM-5 criteria. A responder is a participant who meets the definition of early remission, i.e., ≥ 3 months and < 12 months without meeting DSM-5 criteria while disregarding the result for craving.
- Difference between groups in Clinical Global Impression of Change (CGIC) at Weeks 13, 25, and 33.
- Difference between groups in Patient Global Impression of Change (PGIC) at Weeks 13, 25, and 33.

Study Population:	Approximately 120 adults seeking treatment for their ongoing METH use will be randomized into the study. Approximately 36 of these will be included in the PK subset.
Phase:	2
Description of Sites:	Approximately 10 sites in the US will enroll participants
Description of Study Intervention:	IXT-m200 is a high-affinity chimeric anti-METH monoclonal antibody that is well-tolerated in healthy volunteers and in non-intoxicated participants with METH use disorder. It will be administered at a dose of 1.5 g (approximately 20 mg/kg) and, depending on the results of an interim analysis, up to 3 g (approximately 40 mg/kg). IXT-m200 or placebo treatment will be given by intravenous infusion over 30 minutes. Each participant will receive 6 doses of either placebo or the same dose level of IXT-m200, spaced approximately 4 weeks apart.
Study Duration:	Approximately two years
Participant Duration:	33 weeks

1.2 SCHEMA

1.3 SCHEDULE OF ACTIVITIES (SOA)

1.3.1 MAIN STUDY PARTICIPANT SCHEDULE

Abbreviations: CGIC – Clinical Global Impression of Change; C-SSRS – Columbia Suicide Severity Rating Scale; ET – early termination; HACA – human anti-chimeric antibodies; NA – not applicable; PGIC – Patient Global Impression of Change; PK – pharmacokinetic; TEA – Treatment Effectiveness Assessment

^a Descriptions of assessments are in Section 8.1 (efficacy) or 8.2 (safety).

^b Study Day -1 is the day prior to the first dose. Study Day 1 is the day of the first dose.

^cVital sign measurements will be taken on dosing days starting with a pre-dose measurement (≤ 30 min prior), then 0.25, 0.5, 1, 2, and 4 hours (± 5 min) after dosing starts, and as needed afterward until normalization. Measurements will be obtained once on each non-dosing day. Each test may be repeated once at each time point if the initial result is out of range.

^dLaboratory tests require blood and urine sampling for hematology, serum chemistry, and urinalysis. Samples are to be taken 2-hr post-dose completion (± 10 min) on dose days and once per visit on non-dosing days.

^e ECGs are to be done 30-min post dose completion (± 15 min) on dosing days.

^f Quality of Life Assessments include TEA (at Screening, Days 85, 169, & 225), and PGIC and CGIC (on Days 85, 169, & 225). These assessments are to be done prior to CBT at the Week 13 visit.

^g PK samples are to be taken pre-dose (≤ 30 min prior), then 4 hr (± 10 min) after the start of each infusion on dosing days. Participants should be kept on site until 4 hr post infusion start to collect samples. All other PK samples are to be collected once each visit.

^h Doses will be given over 30 min by intravenous (IV) infusion.

ⁱ AEs will be collected by phone call at 1 day and 1 week (± 2 days) post-dose throughout the study.

^j Recovery coaching will occur weekly via phone or video.

^k Saliva drug screens will be done remotely and monitored by smartphone app.

^l Cytokine samples are to be taken pre-dose (≤ 60 min prior) on each dosing day. If a participant has an infusion reaction, cytokine sampling at 1- and 4-hours post-dose (± 10 min) should be performed.

^m Drug use assessments at Screening include the DSM5 criteria for any drugs used regularly in the past year and questions about route and frequency of METH use.

ⁿ On Days 169 and 225, DSM5 criteria should be used to assess methamphetamine only and for the past 30 days, then for the past 3 months.

^o HACA samples are to be taken pre-dose (≤ 60 min prior) on visit Days 1, 57, and 113, and once on Days 169 and 225.

^p If the participant remains eligible at the end of the Screening visit, enroll them in the DynamiCare system as described in the DynamiCare Site Guide, and schedule the Day 1 visit.

^q If a participant does not have their phone at the Screening visit, the visit should be rescheduled.

1.3.2 PK SUBSET PARTICIPANT SCHEDULE

Assessment ^a	Screening	Dosing (-2/+7 days)										Follow-up (±3 days)			ET			
		≤-1	1				5	9	13	17	21			25	29	33	NA	
Study Week	≤-1	1 ^b					29	57	85	113	141				169	197	225	NA
Study Day	-15 to -1	1 ^b													169	197	225	NA
PK Sample Collection Day			2 (+1)	8 (±2)	15 (±3)	22 (±3)							142 (+1)	148 (±2)	155 (±3)	162 (±3)		
Informed consent	X																	
Initial evaluations ^p																		
Eligibility criteria																		
Demographics																		
Medical history and medications																		
Vital signs ^c																		
Physical exam																		
Psychiatric exam (e.g., C-SSRS)																		
Urine pregnancy test																		
Saliva drug screen																		
Drug use assessment via DSM-5 ^m																		
Laboratory tests ^d	X	X					X	X	X	X	X				X		X	
Electrocardiogram (ECG) ^e	X	X					X	X	X	X	X							
App training																		
App download and tutorial ^q																		
Saliva drug screens (up to 4) ^k	X																	
Recovery coaching ^j																		
Adverse Outcomes Assessment	X							X							X		X	X
Quality of Life Assessments - TEA ^f																		
Quality of Life – PGIC and CGIC ^f								X							X		X	X
METH Use Assessments ⁿ	X														X		X	X
Randomization		X																
Blood for PK ^g	X	X	X	X	X	X	X	X	X	X	X	X	X	X	X	X	X	X
Blood for HACA ^o	X						X		X						X		X	X
Blood for Cytokines ^l	X					X	X	X	X	X								
Dose administration ^h	X					X	X	X	X	X								
Cognitive behavioral therapy	X					X	X	X	X	X						X		
Wellness check																		
Update medical history																		
Update medications																		
Brief psychiatric evaluation																		
Vital signs ^c																		
Targeted physical exam															X		X	X
Urine pregnancy test																		

Assessment ^a	Screening	Dosing (-2/+7 days)										Follow-up (±3 days)			ET			
		≤1	1				5	9	13	17	21			25	29	33	NA	
Study Week	≤1	1					5	9	13	17	21			25	29	33	NA	
Study Day	-15 to -1	1 ^b					29	57	85	113	141				169	197	225	NA
Continuous events AE monitoring ⁱ Recovery coaching ^j Self-report daily drug use by app Random saliva drug screens ^k		Continuous																

Abbreviations: CGIC – Clinical Global Impression of Change; C-SSRS – Columbia Suicide Severity Rating Scale; ET – early termination; HACA – human anti-chimeric antibodies; NA – not applicable; PGIC – Patient Global Impression of Change; PK – pharmacokinetic; TEA – Treatment Effectiveness Assessment

^a Descriptions of assessments are in Section 8.1 (efficacy) or 8.2 (safety).

^b Study Day -1 is the day prior to the first dose. Study Day 1 is the day of the first dose.

^c Vital sign measurements will be taken on dosing days starting with a pre-dose measurement (≤30 min prior), then 0.25, 0.5, 1, 2, and 4 hours (±5 min) after dosing starts, and as needed afterward until normalization. Measurements will be obtained once on each non-dosing day. Each test may be repeated once at each time point if the initial result is out of range.

^d Laboratory tests require blood and urine sampling for hematology, serum chemistry, and urinalysis. Samples are to be taken 2-hr post-dose completion (±10 min) on dose days and once per visit on non-dosing days.

^e ECGs are to be done 30-min post dose completion (±15 min) on dosing days.

^f Quality of Life Assessments include TEA (at Screening, Days 85, 169, & 225), and PGIC and CGIC (on Days 85, 169, & 225). These assessments are to be done prior to CBT at the Week 13 visit.

^g PK samples are to be taken pre-dose (≤30 min prior), then 4 hr (±10 min) after the start of each infusion on dosing days. Participants should be kept on site until 4 hr post infusion start to collect samples. Additional PK samples should be taken on Day 1 and 141 at 1 hr (±10 min) post-start of infusion. All other PK samples are to be collected once each visit.

^h Doses will be given over 30 min by intravenous (IV) infusion.

ⁱ AEs will be collected by phone call at 1 day and 1 week (±2 days) post-dose throughout the study.

^j Recovery coaching will occur weekly via phone or video.

^k Saliva drug screens will be done remotely and monitored by smartphone app.

^l Cytokine samples are to be taken pre-dose (≤60 min prior) on each dosing day. If a participant has an infusion reaction, cytokine sampling at 1- and 4-hours post-dose (±10 min) should be performed.

^m Drug use assessments at Screening include the DSM5 criteria for any drugs used regularly in the past year and questions about route and frequency of METH use.

ⁿ On Days 169 and 225, DSM5 criteria should be used to assess methamphetamine only and for the past 30 days, then for the past 3 months.

^o HACA samples are to be taken pre-dose (≤60 min prior) on visit Days 1, 57, and 113, and once on Days 169 and 225.

^p If the participant remains eligible at the end of the Screening visit, enroll them in the DynamiCare system as described in the DynamiCare Site Guide, and schedule the Day 1 visit.

^q If a participant does not have their phone at the Screening visit, the visit should be rescheduled.

1.3.3 DOSE DISCONTINUED PARTICIPANT SCHEDULE

This schedule will be followed only when a participant has been enrolled and dosed as normal at least once, then dosing is discontinued per section 7.2, but the participant wishes to continue in the study. Priority should be placed on those assessments in bold, blue font.

Assessment ^a	Site Visit (-2/+7 days)					Follow-up (± 3 days)		ET
Study Week	5	9	13	17	21	25	29	33
Study Day	29	57	85	113	141	169	197	225
Laboratory tests ^d	Once at first visit after dose discontinuation							X
Adverse Outcomes Assessment Quality of Life - TEA^f			X			X	X	X
Quality of Life - PGIC & CGIC^f			X			X	X	X
METH Use Assessments ⁿ						X	X	X
Blood for PK ^g	X	X	X	X	X	X	X	X
Blood for HACA ^o		X		X		X	X	X
Cognitive behavioral therapy	X	X	X	X	X		X	
Wellness check								
Update medical history								
Update medications								
Brief psychiatric evaluation	X	X	X	X	X	X	X	X
Vital signs ^c								
Targeted physical exam								
Urine pregnancy test								
Continuous events								
AE monitoringⁱ								
Recovery coaching^j	Continuous							
Self-report daily drug use by app								
Random saliva drug screens^k								

Abbreviations: CGIC – Clinical Global Impression of Change; C-SSRS – Columbia Suicide Severity Rating Scale; ET – early termination; HACA – human anti-chimeric antibodies; NA – not applicable; PGIC – Patient Global Impression of Change; PK – pharmacokinetic; TEA – Treatment Effectiveness Assessment

^a Descriptions of assessments are in Section 8.1 (efficacy) or 8.2 (safety).

^c Vital sign measurements will be obtained once on each non-dosing day. Each test may be repeated once at each time point if the initial result is out of range.

^d Laboratory tests require blood and urine sampling for hematology, serum chemistry, and urinalysis. Samples are to only be taken on the first visit following discontinuation.

^e ECGs are to be done once per visit.

^f Quality of Life Assessments include TEA (at Screening, Days 85, 169, & 225), and PGIC and CGIC (on Days 85, 169, & 225). These assessments are to be done prior to CBT at the Week 13 visit.

^g One PK sample should to be taken per visit; mark this as the pre-dose sample in EDC for visits through Week 21.

^j Recovery coaching will occur weekly via phone or video.

^k Saliva drug screens will be done remotely and monitored by smartphone app.

ⁿ On Days 169 and 225, DSM5 criteria should be used to assess methamphetamine only for the past 30 days, then for the past 3 months.

^o HACA samples are to be taken once each visit.

2 INTRODUCTION

2.1 STUDY RATIONALE

2.1.1 RATIONALE FOR THE COMBINED SAFETY AND EFFICACY STUDY

There are no approved medications for the treatment of METH use disorder (MUD); therefore, any progress toward development of effective medications for MUD is important. The safety of single doses of IXT-m200 has been evaluated in a Phase 1 study of healthy individuals and in a Phase 2 study in otherwise healthy non-treatment seeking participants who use METH. No significant safety events occurred (no SAEs were reported)¹. Furthermore, Good Laboratory Practice (GLP) toxicology studies of repeated doses of IXT-m200 in rats at doses well above the proposed doses in this study have not shown significant toxicity associated with IXT-m200. However, even though the risk of severe complications associated with chimeric monoclonal antibody therapy is low, the risk of infusion reactions is not zero, and establishment of safety and tolerability of repeat doses of IXT-m200 in humans is important. Based on the clinical experience to date with IXT-m200, gathering these safety data in participants with MUD rather than in healthy volunteers is warranted. Given the safety data to date with single doses of IXT-m200 in humans, there is no reason to believe that the safety of repeated doses of IXT-m200 will be different in otherwise healthy individuals seeking treatment for MUD versus healthy non-drug users. Furthermore, the benefit-risk determination of repeat-dose testing of IXT-m200 favors testing in people seeking treatment for METH use, because healthy volunteers would not derive any benefit from such a study. Finally, the use of a serial study design which first evaluates the safety of a lower dose level before proceeding to a higher dose level further decreases any potential safety risk. Therefore, this study is a combined safety and efficacy study in otherwise healthy individuals who are seeking treatment for MUD.

This protocol is designed to evaluate safety of repeated doses of IXT-m200, to evaluate evidence of efficacy in the target population, and to evaluate trends in dose-response relationships for IXT-m200 in preventing or reducing relapse to METH use. Compared to placebo, we hypothesize that IXT-m200 will decrease relapse to stimulant use, improve the signs and symptoms of MUD, and improve participant-reported quality of life in treatment-seeking individuals with MUD.

2.1.2 RATIONALE FOR THE SELECTED POPULATION

Treatment-seeking participants with a history of ongoing METH use will be recruited. Because of the use of treatment-seeking participants in this study, comprehensive and standardized cognitive behavioral therapy (CBT) will be provided to all participants. Persons with MUD, even those who are highly motivated to stop their use and receive treatment, are at high risk for relapse to METH use. Based on the observed safety data from our Phase 2 clinical study with IXT-m200 (STAMPOUT), which studied non-treatment-seeking participants who use METH and in which participants were given controlled doses of METH and then subsequently allowed to resume their habitual METH use, there do not appear to be significant safety risks associated with use of IXT-m200 in this population.

2.2 BACKGROUND

Study Agent

IXT-m200, also called ch-mAb7F9, binds METH with high selectivity and affinity. The product contains a murine METH-binding variable region and the constant domains of a human immunoglobulin G

(IgG) 2κ. This antibody isotype was chosen because of the lower risk of immune response compared to an IgG₁ or IgG₃. IXT-m200 targets METH, does not rely on binding to any endogenous target for its action, and has been well-tolerated in previous clinical studies (see below).

Through the binding of METH in the bloodstream, it is anticipated that IXT-m200 will alter the pharmacokinetics (PK) of METH and decrease concentrations of METH reaching its active sites in the brain. The presence of IXT-m200 should therefore decrease the perceived pleasurable effects of METH. Over the longer term, when combined with behavioral therapy, IXT-m200 should reduce the frequency of METH use over time.

Nonclinical IXT-m200 Effectiveness Summary

A significant body of nonclinical work in rats indicates that IXT-m200 may be effective as a treatment for MUD by altering METH central nervous system effects. The potential human efficacy of IXT-m200 is demonstrated by multiple important *in vivo* preclinical studies using the murine version of the antibody, called mAb7F9. The studies and results are summarized in the Investigator's Brochure (IB).

Nonclinical Safety Summary of the Interaction of IXT-m200 with METH

Four key nonclinical studies were completed in rats to address the potential for IXT-m200 to exacerbate METH effects, specifically cardiovascular effects. These studies were designed to identify potential toxicities resulting from higher blood concentrations of METH in the presence of IXT-m200, or from increased METH consumption by a person in an effort to overcome the reduction of METH effects by the antibody.

In each of the 4 studies, rats were acclimated to high doses of METH over a 14-day period to make them tolerant to high doses of METH, similar to what occurs in people who chronically use METH. By the last day, rats survived three 4 mg/kg doses of METH spaced 4 hours apart. Three days later (Day 17), rats were dosed with 0, 5, or 20 mg/kg IXT-m200. The following day, a series of METH binges used to simulate attempts to surmount the antibody's effects was initiated. On Day 18, rats were given 4 doses of 6 mg/kg METH spaced 2 hours apart. This binge dosing regimen was repeated on Days 21 and 24 for certain studies and groups.

Following the Phase 1 study, a Phase 2 study of IXT-m200 was conducted (STAMPOUT: Study of Antibody for Methamphetamine Outpatient Therapy, NCT03336866). This was a parallel-group, placebo-controlled, double-blind study in otherwise healthy, non-treatment seeking participants who use METH. Participants were required to discriminate METH (30 mg, intravenous) from placebo with a drug effects questionnaire (DEQ) to qualify. Those who qualified received single doses of IXT-m200 (6 or 20 mg/kg) or placebo followed by weekly METH challenges for up to 4 weeks. The challenges consisted of METH (30 mg, intravenous) and placebo, separated by 4 hours. Safety, METH and IXT-m200 PK, and DEQ data were collected for up to 126 days.

56 participants were included in the pharmacokinetic and safety sets, with 20 receiving the placebo, 18 receiving 6 mg/kg IXT-m200, and 18 receiving 20 mg/kg IXT-m200. IXT-m200 was well-tolerated. There were no SAEs and all AEs were grades 1 or 2; all resolved as expected. Importantly, IXT-m200 did not result in substantial hemodynamic changes when compared with METH alone. IXT-m200 met the primary study endpoint, and significantly ($p < 0.001$) altered METH area under the curve (AUC) and Cmax with all METH challenges, up to 30-fold and 8-fold respectively, without altering METH renal elimination (Figure 1). IXT-m200 decreased METH Vd over 9-fold after the first METH challenge (Figure 2). There were favorable trends in DEQ data as well (Figure 3), suggesting that IXT-m200 may also have effects on the reinforcing effects of METH use.

[figure not shown]

Figure 1. METH PK data from STAMPOUT demonstrate IXT-m200 alters METH distribution.
 Area under the curve from time 0 through infinity (AUC_{inf}), maximum METH concentration (C_{max}), volume of distribution (V_d), and cumulative urinary excretion over 36 hr (Ae) data following the day 5 challenge are plotted as mean \pm SD. IXT-m200 (0, 6, or 20 mg/kg, IV) was administered one day prior to METH (30 mg, IV). ***p < 0.0001

[figure not shown]

Figure 2. METH volume of distribution is significantly reduced by IXT-m200 treatment on Day 4 and the effect is still significant 3 weeks later.
 ****p < 0.0001

[figure not shown]

Figure 3. Subject responses on drug effects questionnaires indicate a trend toward reduction of METH effects following an IXT-m200 dose. In this example, subjects were asked “Do you LIKE any of the effects you are feeling right now?” Area under the effect curve data are plotted as the change from Day 1 (baseline).

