3 OBJECTIVES AND ENDPOINTS

OBJECTIVES	ENDPOINTS
Primary	
To evaluate the efficacy of IXT-m200 in preventing or reducing relapse to stimulant use	Percent of 20 weeks abstinent from stimulants following a 4-week grace period (between Week 5 and Week 25) as measured by saliva screens and by self-report via smartphone app.
Secondary	
To evaluate the efficacy of IXT-m200 in increasing the number of participants achieving early remission	Proportion of responders at Week 25 as measured by DSM-5 criteria. A responder is a participant who meets the definition of early remission, i.e., ≥ 3 months and < 12 months without meeting DSM-5 criteria, while disregarding the result for craving.
To evaluate the efficacy of IXT-m200 in improving the proportion of participants achieving stimulant abstinence	Complete abstinence during the last month of study drug treatment (between Week 21 and Week 25), as measured by saliva screens and by self-report via smartphone app.
To evaluate the efficacy of IXT-m200 in improving participant-rated quality of life	Change from screening in participant-rated quality of life as measured by the Treatment Effectiveness Assessment (TEA) at Week 13, 25, and Week 33.
To evaluate the safety of multiple intravenous doses of IXT-m200	Safety and tolerability of IXT-m200 assessed by physical examinations and vital sign, AE, ECG, and clinical laboratory testing.
To evaluate the immunogenicity of multiple doses of IXT-m200	Number of participants with anti-IXT-m200 antibody levels that are confirmed positive and have titers more than three times the minimum required dilution.
Exploratory	
To evaluate the efficacy of IXT-m200 in improving the length of sustained abstinence	Number of sequential weeks of abstinence from the end of treatment visit (Week 25), defined as four weeks after the final planned treatment visit (Week 21) as measured by saliva screens and by self-report via smartphone app.
To evaluate the efficacy of IXT-m200 in improving post-treatment abstinence	Point prevalence abstinence (last 7 days) as measured by saliva screens and by self-report via smartphone app at Week 25, Week 29, and Week 33.
To evaluate the efficacy of IXT-m200 in preventing or reducing relapse to stimulant use	Weekly abstinence from stimulants following a 4-week grace period (between Week 5 and Week 25) as measured by saliva screens.

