9.4.2 ANALYSIS OF THE PRIMARY EFFICACY ENDPOINT(S)

The primary efficacy endpoint is percent of 20 weeks abstinent from stimulants based on saliva screens and by self-report via smartphone app during a 20-week period between Week 5 and Week 25, after a four-week grace period during which relapses may occur. A combination of self-report and saliva screens data and concordance will be used to score each day of the study within these time frames. The primary efficacy endpoint analysis will use the ITT population.

Participants self-report stimulant use on a daily basis; a saliva screen is taken twice a week at two random timepoints. Data that contribute to the primary endpoint will be collected from the day after a participant's Week 5 visit through the next 20 weeks. The SAP will detail the visit windows.

A modified combined self-report and pharmacokinetic-1 (SRPHK1) algorithm⁸ will be used to derive if a day is a "use day" or an "abstinent day". Briefly the rules of the algorithm (as listed in Somoza et al., 2008 with minor modifications) are:

1. Always label self-reported use days as use days.
2. Label any day covered by a positive saliva screen as a use day. However, if that day is a self-reported no-use day and one of the one or two previous days was self-reported as a use day, assign the saliva-based use to the self-reported use day. If self-report is missing for the day prior to the positive saliva sample, the day will be considered a use day.
3. Label as missing any self-reported no-use days not followed by a saliva sample within 7 days. Also label as missing any day having a missing self-report and no saliva-based indication of use or no use.
4. Treat all other self-reported no-use days (temporarily) as "unknown".
5. Treat "unknown" days as described below:
 - a. Calculate the "concordance rate" as follows:
 - (1) determine the number of instances in which a day has been assigned a saliva screen status of use but the participant reports no use;
 - (2) divide this number by the total number of saliva samples;
 - (3) subtract the resulting fraction from 1.
 - b. If the concordance rate is ≥ 0.7 (i.e., if we can trust that the participant tells the truth in his or her self-report), label all remaining "unknown" days as no-use days; otherwise label all remaining "unknown" days as missing.
6. Weeks with missing values for every day will be imputed as a non-abstinent week.

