1.1. Objectives, Endpoints, and Estimands

The following Table 2 lists the primary and secondary efficacy objectives of the study, along with the endpoints that will be measured, the clinical question to be addressed, as well as the estimand. An estimand is defined in the ICH E9(R1) guidance as "...the target of estimation to address the scientific question of interest posed by the trial objective."

Table 2 Primary and Secondary Efficacy Objectives, Endpoints and Estimands

Primary		
Objective: To evaluate the efficacy of IXT-m200 in preventing or	Endpoints: Percent of 20 weeks abstinent from stimulants following a 4-week grace period (between Week 5 and Week 25) as measured by saliva screens.	
reducing relapse to stimulant use.	Clinical Question: Does adding IXT-m200 to standardized cognitive behavioral therapy (CBT) program improve the percent of 20 weeks abstinent from stimulants following a 4-week grace period, relative to the CBT program alone, in treatment-seeking participants, regardless of IXT-m200 interruption or discontinuation, for any reason?	
	Estimand: The difference in group means between the IXT-m200 and placebo groups for the percent of 20 weeks abstinent from stimulants following a 4-week grace period as measured by saliva screens in treatment-seeking individuals with MUD. All observations will be used, regardless of whether a participant discontinued treatment early. All missing values will be imputed assuming the participant is not abstinent.	
	Secondary	
Objective: To evaluate the efficacy of IXT-m200 in improving	Endpoints: Change from screening in participant-rated quality of life as measured by the Treatment Effectiveness Assessment (TEA) at Week 13, 25, and Week 33.	
participant-rated quality of life.	Clinical Question: Does adding IXT-m200 to standardized CBT program improve the change from screening in participant-rated quality of life relative to the CBT program alone in treatment-seeking participants regardless of IXT-m200 interruption or discontinuation, for any reason?	
	Estimand: The difference in group medians for the change from screening in participant-rated quality of life at Week 13, 25, and 33 between the IXT-m200 and placebo groups. All observations will be used, regardless of whether a participant discontinued treatment early. Missing values will not be imputed.	

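### The SAP scores the primary endpoint from saliva screens alone, drops the protocol's self-report component without declaring it, and plans no paired check that screens detect use equally in both arms

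*Protocol*

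**What the plan says.** **Protocol.** Section 3 defines the primary endpoint "as measured by saliva screens and by self-report via smartphone app". Section 9.4.2 explains the scoring: "A combination of self-report and saliva screens data and concordance will be used to score each day of the study". The first rule of its modified SRPHK1 algorithm is "Always label self-reported use days as use days", so a negative screen cannot cancel an admitted use day.

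**SAP.** Section 1 states that the SAP prevails over the protocol's statistical sections where they differ. Table 2 gives the primary endpoint as "Percent of 20 weeks abstinent from stimulants following a 4-week grace period (between Week 5 and Week 25) as measured by saliva screens", and the estimand uses the same source. The day-scoring algorithm and the concordance rate do not appear in the primary analysis (4.6.1). The sensitivity analyses (4.6.2) cover only non-imputation of missing values and, conditionally, the per-protocol set. Section 4.13 says that nothing planned in the protocol has been altered.

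**Pharmacology.** Protocol 2.2 reports from the earlier Phase 2 study that the antibody "altered METH area under the curve (AUC) and Cmax with all METH challenges, up to 30-fold and 8-fold respectively", and that "IXT-m200 decreased METH Vd over 9-fold after the first METH challenge". The Figure 2 caption adds that the effect on volume of distribution was still significant three weeks later.

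**The concern.** The treatment acts on a substance that the outcome test measures. The screens are qualitative (Protocol 8.1.2), so a change in how much METH reaches saliva, or how long it stays there, could turn a positive screen negative or the reverse. Doses are four weeks apart and the antibody's half-life is about 18 days (Protocol 2.2), so altered disposition could plausibly extend over much of Weeks 5 to 25.

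If detection differs by arm, part of the primary difference reflects the test and not drug use. The protocol's rule on self-reported use limited one form of this, a missed detection. The SAP removed that protection and put no check in its place. SAP 4.6.1 would declare efficacy on nominal significance of this endpoint. Sequential weeks, point prevalence and last-month abstinence are also saliva-only in SAP Table 3, so they could not reveal the problem.

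**Working it through.** **1. The two documents side by side.**

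| Item | Protocol 3 and 9.4.2 | SAP Table 2, 4.6.1, 4.6.2, 4.13 |
|---|---|---|
| Source of primary endpoint | Saliva and self-report | Saliva |
| Self-reported use, negative screen | Use day | No effect on primary |
| Saliva versus self-report concordance | Computed per participant | Not computed |
| Change declared | – | None |

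The protocol's concordance rate counts only positive screens with denied use, and it is not compared by arm. Restoring it would not supply the missing check.

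**2. The plan's detectable difference.** Cohort 2 was never enrolled (SAP 1.2), so 40 versus 20 applies. A two-sample t-test, two-sided 5%, has 80% power at 0.780 SD, which matches the SAP's 0.78. In points: 0.78 × 20 = 15.6, 0.78 × 25 = 19.5, 0.78 × 30 = 23.4.

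**3. Illustration of what unequal detection could do.** None of the inputs below is in the documents.

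- q = true share of use weeks, the same in both arms (no drug effect)
- s = chance that one screen is positive in a use week
- c = share of weeks with both screens done

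Two screens are planned per week. Take the week as non-abstinent if either is positive or missed, and take the screens as independent with no false positives:

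apparent abstinence = c × [(1 − q) + q(1 − s)²]

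The spurious difference is c × q × [(1 − s_active)² − (1 − s_placebo)²]. With c = 1, q = 0.7 and s_placebo = 0.9:

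| s_active | Calculation | Shift (points) | Chance of p < 0.05, SD 20% | SD 30% |
|---|---|---|---|---|
| 0.8 | 0.7 × (0.04 − 0.01) | 2.1 | 6.6% | 5.7% |
| 0.7 | 0.7 × (0.09 − 0.01) | 5.6 | 17.1% | 10.3% |
| 0.6 | 0.7 × (0.16 − 0.01) | 10.5 | 47.0% | 24.2% |
| 0.5 | 0.7 × (0.25 − 0.01) | 16.8 | 85.5% | 52.0% |

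The nominal rate is 5%. Swapping the sensitivities between arms reverses the sign. At s_active = 0.5 the shift runs from 0.5 × 0.24 = 12.0 points (q = 0.5) to 0.9 × 0.24 = 21.6 (q = 0.9). With c = 0.5 every shift halves.

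To create the full 15.6 points, s_active must equal 1 − √(0.156/q + 0.01): about 0.43, 0.52 or 0.57 for q = 0.5, 0.7 or 0.9. That is a large loss from 0.9. Prolonged detection is not in this model. It would mainly misclassify non-use weeks and so scale with 1 − q.

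**The case against.** - **The mechanism is inferred.** The pharmacokinetic results follow 30 mg intravenous challenges and describe systemic METH and urinary excretion. No saliva result is given. The fold changes are maxima, and the same sentence reads "up to 30-fold and 8-fold respectively, without altering METH renal elimination". Urine is not saliva, so this does not settle the matter either way. It stands as a limit: the documents support a possible risk only.
- **Self-report is analysed.** SAP Table 3 and 4.8 compare percent of days abstinent by self-report between arms over the same weeks. They also give responder curves by arm for self-report and for saliva, and 4.1 says the endpoints deliberately vary the definition of response. A gross divergence between the two sources would show. This stands, but the measures are in different units and are never paired with screens in the same participant and week.
- **Missingness dilutes the effect.** A missed test, and every week after withdrawal, scores as non-abstinent, and dropout may reach 50% (SAP 2.2). Detection cannot matter in those weeks. This stands.
- **The trial is exploratory, with nominal p-values.** This stands, and it lowers the stakes.

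Four stronger readings are tempting, and the documents do not support them:

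- **The endpoint is METH detection alone.** It concerns stimulants, and the panel includes amphetamine and cocaine. The SAP names the methamphetamine result only for the plot and does not say which analytes make a week non-abstinent.
- **The endpoint is biased in the drug's favour.** The direction is unknown.
- **The result cannot be interpreted.** The by-arm self-report analyses give some independent evidence.
- **The bias is 3 to 12 points.** A reader might multiply an assumed 60% of use weeks by an assumed 5 to 20 point gap in weekly detection (0.6 × 5 = 3, 0.6 × 20 = 12). That ignores two tests per week, missed-test weeks and false positives in non-use weeks.

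**Conclusion.** Two facts are certain from the text. The SAP replaced a combined saliva and self-report endpoint with a saliva-only one while declaring no change, and it plans no paired comparison of the two sources by arm. Unequal detection is an unexamined risk, not a demonstrated bias. Its size and direction cannot be derived from the documents.

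The illustration rests wholly on assumed q, s and c, independent screens and no false positives. Under those assumptions a modest loss of sensitivity moves the result little (2.1 points), and only a loss to roughly 0.4 to 0.6 per test reaches the 15.6-point detectable difference. The point is a cheap improvement worth making, not a reason to discard the primary analysis.

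**What to change.** In SAP 4.6.2, pre-specify before database lock:

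1. A descriptive table by arm of the share of screens positive within 1 to 2 days of self-reported use, and the share positive after self-reported non-use, with numbers of screens and participants. At two screens a week for 20 weeks there are at most 40 × 40 = 1,600 active and 20 × 40 = 800 placebo screens, clustered within participants.
2. A repeat of the primary ANCOVA on the protocol's combined endpoint, as a sensitivity analysis reported alongside the saliva-only result. Which result is interpreted should not depend on the table. The protocol algorithm also handles missing data differently, so state which missing-data rule applies.

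Also correct SAP 4.13 to declare the change of source, and cite any saliva METH data with the antibody present if they exist.

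**Cost.** Programming and text only. Both data sources are already collected, and SAP section 1 lets added supportive analyses be described in the study report without an amendment.

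**Downsides.** Self-report is imperfect. Positivity on reported-use days also depends on the amount used, so a difference would not isolate test behaviour. Counting either source corrects missed detection but not prolonged detection. The protocol's algorithm reassigns a positive screen only to a self-reported use day one or two days earlier.
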